2.3.2 Potential Benefits

Clinicians and the students/patients they serve will be offered a potentially effective intervention for collaboratively monitoring their progress in mental health treatment over time. Clinician participants who use the measurement-based care processes that they will be trained and supported to use will have the opportunity to learn an evidence-based practice they can use with any of their patients as they wish. Clinicians will also receive one year user access to Better Outcomes Now (www.betteroutcomesnow.com) which is an online system to collect, score, view and discuss student progress on the Outcome Rating Scale and Session Rating Scale. They will receive training and consultation on how to use this evidence-based, practical system with students and families, whether you are meeting with them virtually or in person.

Children and parents who engage in the measurement-based care processes that clinicians will be trained and supported to use may experience greater therapist/patient alliance and improvement in symptoms and functioning at the end of treatment. We feel the potential benefits to be gained outweighs the risks of the study.

3 Study Purpose and Objectives

3.1 Hypothesis

Hypothesis 1: Clinicians' ratings of MBC implementation outcomes will increase following implementation strategies provided as compared to ratings during the baseline period. (Primary Objective)

Hypothesis 2: MBC fidelity (per MBC feedback system review) and use (per clinician self-report) will increase following implementation strategies provided as compared to ratings during the baseline period, with documentation of measure collection more prevalent than documentation of discussing progress or changing the treatment plan in accordance with measures. (Primary Objective)

Hypothesis 3: MBC fidelity and use will be positively associated with engagement and mental health symptom and functioning progress over time. (Secondary Objective)

Although underpowered to establish outcomes as a result of strategies applied with certainty, this pilot will provide mentored research experience and preliminary data for planning a future large-scale hybrid trial.

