Implementation outcomes are selected from a published taxonomy of outcomes include acceptability, appropriateness, feasibility and fidelity. **Acceptability, appropriateness, and feasibility** will be measured by clinician self-report on the Acceptability of Intervention Measure (AIM), Intervention Appropriateness Measure (IAM), and Feasibility of Intervention Measure (FIM) via web-based, clinician-report survey. These 4-item measures were developed based on input from 36 implementation scientists and 27 mental health professionals; structural validity, test-retest reliability, and sensitivity to change have been established. **MBC use (fidelity)** will be evaluated by chart review in BON for evidence of two progress monitoring measures, the Session Rating Scale 3.0 (SRS) and Outcomes Rating Scale 3.0 (ORS). The MBC training provided as part of this study will include how to use MBC and document it in BON. The ORS will be completed before each session to assess prior-week functioning, and the SRS will be completed at the end of the session to assess student/parent perceptions of alliance with the clinician.

Secondary and Exploratory Outcome Variables

The secondary objective of this study is to examine effectiveness outcomes.

Effectiveness outcomes of MBC will be measured using actual scores on the SRS and ORS, as documented in the student's service record. The SRS and ORS are part of the Partners for Change Outcome Management System (PCOMS), a system used to enhance patient involvement in mental health services and improve therapeutic alliance and treatment progress. **Student engagement** will be measured by the SRS. **Parent engagement** will be measured by the Therapeutic Alliance Scales for Caregivers and Parents. **Symptoms and functioning** will be measured using the ORS. Emotional and behavioral symptoms will also be measured by the Pediatric Symptom Checklist, 35-item version (PSC-35) which has well-established reliability and validity to assess and monitor progress of internalizing and externalizing symptoms for children ages 4-18. The Therapeutic Alliance Scales for Caregivers and Parents and the PSC-35 will be collected directly from parents/guardians over the phone at baseline and follow-up intervals.

Study Population

This study plans to enroll up to 150 parents/legal guardians of children or adolescents receiving SMH treatment from one of the 50 participating clinicians. We anticipate SMH

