4.1.1 General Design Description

A clustered, multiple-baseline design will be used to examine the impact of the implementation support condition on clinicians' fidelity, use and ratings of MBC appropriateness, acceptability and fidelity. Approximately 50 SMH clinicians will be recruited to participate from two school districts. All clinicians will receive the same implementation supports; there is no random assignment to condition. Following an initial control period of at least 1 month, school districts will start receiving implementation supports. During the initial control period, baseline MBC use, attitudes, acceptability, feasibility and appropriateness (per clinician self-report) will be collected, as well as needs assessment data from clinician surveys to inform necessary adjustments to the implementation supports. Baseline engagement and student outcomes will be collected after initial clinician training session. MBC implementation outcomes (i.e., MBC use, attitudes, acceptability, appropriateness, and feasibility), engagement and student outcomes will be collected at 3-month and 6-month follow-up during intervention supports, plus a 9-month follow-up interval. This allows clinicians in the two school districts to be compared to each other and to their own baseline. The primary comparison is pre-post ratings of implementation outcomes for all N=50 clinicians. The secondary comparisons are pre-post ratings of engagement and student outcomes, and between-agency differences.

Study Date Range and Duration

This study is expected to last approximately one calendar year from recruitment to follow-up, aligned with the 2021-2022 and 2022-23 academic years as the participating sites are school districts. Clinicians will start training and consultation in the fall of 2021 or 2022 and parents/guardians will be recruited in the fall of 2021 or 2022. Data collection will occur at baseline, 3 months, 6 months and 9 months.

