5.1.1 Data Collection

Data Sources. Data sourced for this study will include computerized and hard copy research records. Any hard copy research records will be scanned and saved electronically on a Yale secure server before shredding the paper copy. Data sources will include:

- (1) Quantitative data from clinician self-report surveys about **MBC acceptability, appropriateness, and feasibility** as well as **MBC use** every three months during implementation supports. Some qualitative feedback will also be solicited on the survey for clinicians to expand on any details the standardized measures of these implementation outcomes could not capture. (*Primary outcome variables*)
- (2) Quantitative data on **MBC use (clinician fidelity)** coded by chart review protocol, in which fidelity includes presence of SRS and ORS measures in the online BON/PCOMS system to approximate fidelity per clinician. (*Primary outcome variables*)
- (3) Quantitative data on proximal and distal **student engagement and functioning outcomes** collected by the clinician as part of the project, retrieved from medical records and/or the PCOMS system directly (SRS, ORS). (*Secondary outcome variables*)
- (4) Quantitative data on **parent engagement** and distal **student symptoms** collected by the study team as part of the project from parents over the phone (Therapeutic Alliance Scales, PSC-35). (*Secondary outcome variables*)
- (5) Tracking data on parent **recruitment, clinician attendance/engagement in implementation supports**. (*Implementation mechanisms*)

Data sources 1-4 above refer to primary and secondary outcomes of explicit focus in the analyses and are listed in the table below.

Table 1. List of Measures and Data Collection Methods

Outcome	Measure	Method	Reporter	Interval
MBC Acceptability (content, complexity, relative advantage)	Acceptability of Intervention Measure (AIM)	Online survey	Clinician	Pre-training 3M follow up 6M follow up 9M follow up
MBC Appropriateness (for setting, provider, students served)	Intervention Appropriateness Measure (IAM)			
Feasibility (for SMH practice)	Feasibility of Intervention Measure (FIM)			
MBC Use	Current Assessment Practice Evaluation - Revised (CAPER)			

MBC Attitudes	Attitudes toward Standardized Assessment – Monitoring and Feedback (ASA-MF)			
Implementation Determinants	MBC Feedback Form – Assess Barriers and Facilitators			Pre-training

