ORS/SRS Acceptability	Usage Rating Profile – Assessment (URP-A)			3M follow up 6M follow up 9M follow up
Fidelity (MBC Use)	Retrospective coding of PCOMS measures (SRS, ORS)	Chart review and/or BON system	Study Team	Monthly
Student Engagement	Session Rating Scale (SRS)			
Student Functioning	Outcome Rating Scale (ORS)			
Student Symptoms	Pediatric Symptom Checklist (PSC-35)	Phone	Parent	Baseline* 3M follow up 6M follow up 9M follow up
Parent Engagement	Therapeutic Alliance Scales for Caregivers and Parents			

**after clinician consent, near initial clinician training*

Secure Data Recording and Maintenance:

Online survey data will be maintained in the PI's Yale Qualtrics account, accessible only by members of the study team listed on the IRB protocol. Online survey data will be downloaded and maintained on secure Yale storage servers and networks (i.e., Yale Box, network drive). Clinicians will provide their identifying information (name, email address) when they consent as well as a secure 4-digit anonymous code. They will be asked to submit this same 4-digit code with each follow-up survey. This will ensure the study team can track individual clinician responses over time, but each survey is completed confidentially. A password-protected Excel file including clinician identifying information and 4-digit codes will be maintained on secure Yale storage servers and networks, accessible only to study team members.

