Results of all the above analyses will be expressed in terms of 95% confidence intervals for effects and contrasts which together with estimates of intra-clinician correlation and variance will inform the power analysis for a larger trial.

Mixed Methods Analyses

For (2) we will also analyze chart review data. We will develop and test our MBC fidelity rubric on a subset of consented students at midpoint in the school year to assess intercoder reliability, test our coding form on the text of progress notes, and refine both our coding form and process for accessing records in an efficient, reliable manner. These analyses will yield mixed methods data on clinician use of MBC to be triangulated with clinician self-reported use of MBC on surveys to evaluate relative advantages and disadvantages of these methods to assess use of MBC. Qualitative data generated from chart reviews will be analyzed using Rapid Qualitative Analysis whereby two coders plus the PI will create summaries of chart review findings per student using a standard summary form, which is then entered into a matrix for the entire sample to be reviewed, coded iteratively, and synthesized for main themes and sub codes. These findings will directly inform the future R01 application methods regarding the collection and use of chart review and/or clinician surveys to assess MBC use/fidelity following implementation supports.

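### Hypothesis 2 predicts a rise in BON-reviewed fidelity over the baseline period, but no pre-training BON measurement is scheduled; only self-reported use (CAPER) has one

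*Combined protocol and SAP*

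**What the plan says.** Section 3.1 places Hypothesis 2 under the primary objective. Its first part is that "MBC fidelity (per MBC feedback system review) and use (per clinician self-report) will increase following implementation strategies provided as compared to ratings" from the baseline period. Its second part is that collecting measures will be documented more often than discussing progress or changing the treatment plan.

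Section 5.1.1 lists two separate primary outcome variables for use of measurement-based care. One is clinician self-report. The other is coded by the study team, where "fidelity includes presence of SRS and ORS measures in the online BON/PCOMS system to approximate fidelity per clinician".

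On timing, section 4.1.1 says: "During the initial control period, baseline MBC use, attitudes, acceptability, feasibility and appropriateness (per clinician self-report) will be collected". The Synopsis (Study Design) lists the same self-reported baseline. Table 1 puts the CAPER in the online survey block, with points before training and at 3, 6 and 9 months. It gives the interval for study-team fidelity coding as monthly, with no start month.

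On the system itself, the Synopsis says: "The MBC training provided as part of this study will include how to use MBC and document it in BON". Section 2.3.2 says: "Clinicians will also receive one year user access to Better Outcomes Now". Section 5.2 also describes BON as a system to which the project grants access.

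**The concern.** A directional claim against baseline needs a baseline measured in the same way. The hypothesis puts two measures in one sentence as if both had one. If the BON part is left as it is, the report must either leave it untested or treat the pre-training value as zero because clinicians had no access. In the second case fidelity has increased as soon as a clinician records anything, and a primary hypothesis can be declared supported on a result that says little about the extent of use.

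The project is a pilot meant to inform a larger trial. What that trial needs from BON is how much clinicians used the measures each month and whether use held up. Sections 5.1.1 and 5.3.1 do not define that summary: the BON data are to approximate or estimate fidelity per clinician, without saying how.

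**Working it through.** The plan states no figure on this point, so the check is of the schedule, followed by short arithmetic on what an increase over zero would mean.

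**Step 1: planned measurement points for the two halves of the contrast.**

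| Component | Source | Planned timing | Scheduled before training |
|---|---|---|---|
| Self-reported use (CAPER) | Clinician survey | Before training, 3, 6 and 9 months (Table 1; section 5.2 confirms a survey before the first training) | 1 of 4 |
| Fidelity | Chart review and/or BON, study team | Monthly, start not stated (Table 1) | 0 |

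**Step 2: could another part of the plan supply a BON baseline?**

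- The control-period data in the Synopsis and section 4.1.1 are clinician self-report plus a needs assessment.
- Section 4.1.1 places the baseline for engagement and student outcomes, which include SRS and ORS scores, after the first training session.
- The session-level model in section 5.3.1 has a baseline time level, but it concerns ORS and SRS scores as effectiveness outcomes, not fidelity.
- The chart items that section 5.1.1 gives as examples are diagnosis, entry date, goals and number of sessions. None records whether an ORS or SRS was completed.

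None of these schedules a pre-training fidelity value.

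**Step 3: what counts as an increase over zero.** If the pre-training value is 0, change = post-training level - 0 = post-training level. The estimate is the same number either way; only the word increase loses its content.

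To give a scale: section 5.2 asks for measures 2-4 times per month with at least five students, and the Synopsis expects both scales at a session ("The ORS will be completed before each session to assess prior-week functioning, and the SRS will be completed at the end of the session"). Section 5.2 can be read in two ways.

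- Per student: 5 x 2 = 10 to 5 x 4 = 20 ORS+SRS pairs per clinician-month. One pair is 1/20 = 5% to 1/10 = 10% of the request.
- Per clinician: 2 to 4 pairs per clinician-month. One pair is 1/4 = 25% to 1/2 = 50%.

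Under either reading, a single pair is an increase over zero.

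**Step 4: why the summary should be monthly.** Suppose a clinician measures five students once each in month 1 and then stops. A cumulative count of students with both scales reads 5 of 5 from then on. Counted by month over the six months of consultation, it reads 5, 0, 0, 0, 0, 0, an average of 5/6 = 0.83 students per month against the five requested. Only the monthly count shows that use stopped.

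**The case against.** The strongest reply is that this is wording with little consequence. Section 5.3.1 expresses results as 95% confidence intervals to inform the power analysis of a larger trial, section 3.1 calls the pilot underpowered, and no alpha or BON pre-post test is planned. The growth model in section 5.3.1 is worded for outcomes that clinicians report on surveys, and section 4.1.1 describes the primary comparison as one of ratings. All of this stands, and it limits the point to what may be concluded. It does not remove it: BON-coded fidelity is a named primary outcome variable, and the hypothesis attached to it cannot be evaluated as written.

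Four stronger readings are tempting, and the documents do not support them.

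- *The plan rules out a pre-training BON measurement.* It does not. Coding is retrospective and monthly with no start given, so a control-period month is not expressly excluded. None is scheduled.
- *The timing of the fidelity rubric proves there is no baseline.* The plan says "We will develop and test our MBC fidelity rubric on a subset of consented students at midpoint in the school year". When a rubric is developed does not fix which months are later coded with it.
- *Statistical significance would be nearly automatic.* With all 50 clinicians set to zero at baseline, an exact two-sided McNemar test on any entry gives p = 2 x 0.5^6 = 0.031 once 6 of 50 (12%) make one; with 5 of 50, p = 2 x 0.5^5 = 0.0625. The plan contains no such test, so this does not describe its analysis.
- *The whole of Hypothesis 2 fails.* The CAPER contrast has its baseline, and the prediction about collection compared with discussion and plan change needs none.

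**Conclusion.** The point holds for the BON half of Hypothesis 2 only. No section schedules a pre-training BON measurement, so the predicted increase is either undefined or made against zero. The zero is an inference from project-granted access and project training; the documents do not say whether any clinician used BON earlier. If it is right, the estimated level is unharmed, and what is lost is the meaning of the directional conclusion.

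The missing baseline does not depend on the arithmetic. The 5-10% and 25-50% figures only illustrate how little use would count as an increase, and they depend on which reading of section 5.2 is taken. This should be corrected because it changes what can be concluded on a primary outcome, but it does not threaten the self-report analyses.

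**What to change.** 1. In Hypothesis 2, limit the increase from baseline to CAPER self-reported use (before training, 3, 6 and 9 months). Leave the second part of the hypothesis as it stands.
2. State BON fidelity as a post-training outcome, summarised per clinician and per month. One suitable measure is the number of students with both an ORS and an SRS recorded in that month, set against the request for at least five. Report the level with a 95% confidence interval and the monthly trend, using the clinician-level aggregates described in section 5.1.1. If a pairs-per-month benchmark is added, state the reading of section 5.2 behind it: 10-20 per student, or 2-4 per clinician. Display by district is already foreseen in section 6.15 and needs no further change.
3. State whether any clinician had BON access before training. If some did, say how their earlier entries will be treated.

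The cost is a reworded hypothesis and one defined summary, drawn from coding that Table 1 already plans; no new data are collected. The downside is that BON fidelity becomes a post-training level and trend, with no before-and-after evidence on the implementation supports. That evidence would rest on self-report alone.

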3.2 Primary Objective

The primary objective of this study is to determine whether a multi-method implementation support package will help school-based mental health clinicians use MBC strategies, as measured by MBC implementation outcomes (e.g., feasibility, acceptability, appropriateness, and use or fidelity) with K-12 students. The multi-method implementation strategy package was designed based on prior research, and includes initial training, ongoing monthly consultation, tailoring implementation supports to needs identified by clinicians prior to implementation, and working with school district leadership to promote implementation (e.g., by reducing burdensome documentation requirements). I hypothesize that clinicians' ratings of MBC implementation outcomes will increase following the implementation strategies provided as compared to their ratings during the baseline period without strategies and fidelity (i.e., use of) MBC with students served in SMH treatment.

3.3 Secondary Objective

The secondary objective of this study is to determine whether MBC implementation in schools is associated with engagement in treatment and student outcomes (i.e., reduction in symptoms and improvements in functioning) over the course of SMH treatment.

4 Study Design

4.1.1 General Design Description

A clustered, multiple-baseline design will be used to examine the impact of the implementation support condition on clinicians' fidelity, use and ratings of MBC appropriateness, acceptability and fidelity. Approximately 50 SMH clinicians will be recruited to participate from two school districts. All clinicians will receive the same implementation supports; there is no random assignment to condition. Following an initial control period of at least 1 month, school districts will start receiving implementation supports. During the initial control period, baseline MBC use, attitudes, acceptability, feasibility and appropriateness (per clinician self-report) will be collected, as well as needs assessment data from clinician surveys to inform necessary adjustments to the implementation supports. Baseline engagement and student outcomes will be collected after initial clinician training session. MBC implementation outcomes (i.e., MBC use, attitudes, acceptability, appropriateness, and feasibility), engagement and student outcomes will be collected at 3-month and 6-month follow-up during intervention supports, plus a 9-month follow-up interval. This allows clinicians in the two school districts to be compared to each other and to their own baseline. The primary comparison is pre-post ratings of implementation outcomes for all N=50 clinicians. The secondary comparisons are pre-post ratings of engagement and student outcomes, and between-agency differences.

Study Date Range and Duration

This study is expected to last approximately one calendar year from recruitment to follow-up, aligned with the 2021-2022 and 2022-23 academic years as the participating sites are school districts. Clinicians will start training and consultation in the fall of 2021 or 2022 and parents/guardians will be recruited in the fall of 2021 or 2022. Data collection will occur at baseline, 3 months, 6 months and 9 months.

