Study Design

A clustered, multiple-baseline design will be used to examine the impact of implementation support on clinicians' fidelity, use and ratings of MBC appropriateness, acceptability and fidelity. Approximately 50 SMH clinicians will participate from up to three school districts as a part of their regular professional development activities. In these school districts, measurement based care implementation is a district-wide quality improvement initiative. All clinicians will receive the same implementation supports; there is no random assignment to condition. Following an initial control period of at least 1 month, school districts will start receiving implementation supports. Baseline MBC use, attitudes, acceptability, feasibility and appropriateness (per clinician self-report) will be collected, as well as needs assessment data from clinician surveys to inform necessary adjustments to the implementation supports. Baseline engagement and student outcomes will be collected after initial clinician training session. MBC implementation outcomes (i.e., MBC use, attitudes, acceptability, appropriateness, and feasibility), engagement and student outcomes will be collected at 3-month and 6-month follow-up during intervention supports, plus a 9-month follow-up interval. This allows clinicians in the school districts to be compared to each other and to their own baseline. The primary comparison is pre-post ratings of implementation outcomes for all N=50 clinicians. The secondary comparisons are pre-post ratings of engagement and student outcomes, and between-agency differences.

Clinicians will receive a 3-hour professional development on MBC in Fall 2022 that is required by the three participating school districts. Monthly, post-training group consultation calls will be conducted for 6-months, and online, self-report surveys will be collected at baseline, 3-month, 6-month and 9-month intervals. Clinicians will be asked to implement measurement-based care, using the Better Outcomes Now (BON) online feedback system, with at least 5 students each. Data in BON are deidentified and this activity is part of routine care provided by clinicians, so does not require special consent. These data will also be used to inform group consultation supporting clinicians' practices.

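### The design is labelled clustered multiple-baseline, but clinician ratings have one pre-training survey and no stated district stagger, so the primary comparison is single-group pre-post and cannot attribute change to the package.

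*Combined protocol and SAP*

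**What the plan says.** - **Label.** The Synopsis (Study Design) and section 4.1.1 both call the design clustered and multiple-baseline. Section 4.1.1: "A clustered, multiple-baseline design will be used to examine the impact of the implementation support condition".
- **Allocation.** "All clinicians will receive the same implementation supports; there is no random assignment to condition" (4.1.1).
- **Control period.** "Following an initial control period of at least 1 month, school districts will start receiving implementation supports" (4.1.1). No length or start date is given for any particular district.
- **Survey schedule.** For the acceptability, appropriateness and feasibility ratings, Table 1 in section 5.1.1 gives the interval as "Pre-training 3M follow up 6M follow up 9M follow up". Section 5.2 likewise lists four surveys, one of them before training. The Synopsis (Study Schedule) and section 5.1 add a survey after training, which is not a second baseline.
- **Start of training.** The Synopsis says "Clinicians will receive a 3-hour professional development on MBC in Fall 2022", as a requirement of the three participating districts. The date paragraphs in the Synopsis and after 4.1.1 instead refer to cohorts starting in fall 2021 or fall 2022.
- **Comparisons.** "This allows clinicians in the two school districts to be compared to each other and to their own baseline" (4.1.1). The same section makes the pooled pre-post change in all 50 clinicians primary, and lists between-agency differences as secondary.
- **Objective.** Section 3.2 aims to "determine whether a multi-method implementation support package will help school-based mental health clinicians use MBC strategies".
- **Analysis.** In section 5.3.1 the primary model is a growth model with time nested within clinician. An intervention-or-control term appears only in the session-level ORS/SRS model, together with periods MP1, 2 or 3.

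**The concern.** A multiple-baseline design supports attribution in two ways. Several pre-intervention measurements show what the outcome was doing before anything changed. Staggered starts let one cluster serve as a concurrent control while another is already under the intervention. If both are absent, any movement over the school year, any effect of answering the same items again, and any expectation raised by a district-wide initiative are counted as effects of the supports. Comparing districts that all receive the supports does not remove a trend they share.

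What is at stake is the strength of the conclusion. The label and the wording of the primary objective promise an attribution that the data cannot give. Section 5.3.1 says the results will inform the power analysis for a larger trial, so drift read as effect would be carried into that trial's assumptions.

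**Working it through.** The plan states no power calculation, SD, correlation or test level, so there is no figure to reproduce. The check is structural, followed by an illustration.

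**1. What a multiple-baseline design needs, against what is specified**

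- Repeated pre-training measurements: one survey (Table 1; section 5.2).
- Start times that differ by district: none stated.
- Clinicians measured untrained while others are under supports: none described. Each cohort takes part within its own school year.
- A model term that uses the stagger: none. The primary model has time, clinician and covariates (school district among them), but no condition or staggered-start term.

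**2. Can the package be separated from calendar time?**

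Take a design matrix with an intercept, district or cohort indicators, a free effect for each calendar survey time, and a treated indicator. The package effect is estimable only if adding the treated column raises the rank. The placement of the pre-training survey one month before training is an assumption.

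| Schedule | Columns | Rank | Package effect |
|---|---|---|---|
| Three districts start together, 1 pre and 3 post surveys | 7 | 6 | Aliased with calendar time |
| Two cohorts 12 months apart, 1 pre and 3 post each | 10 | 8 | Aliased |
| Two districts offset by 1 month (assumed), 1 pre and 3 post each | 10 | 8 | Aliased |
| Assumed true multiple baseline: starts 3 months apart, monthly surveys | 13 | 13 | Separable |

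The column count for the first row is 1 intercept + 2 district + 3 time + 1 treated = 7. For the second and third it is 1 + 1 + 7 + 1 = 10, because the two clusters share no survey time.

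If calendar time is forced to be linear, the effect becomes estimable in the first three rows. That is by assumption only, because one pre-training point cannot show whether a trend existed. The table covers these schedules and no others. A longer offset that placed one district's pre-training survey beside another's follow-up could behave differently, which is why actual dates matter.

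**3. Illustrative size**

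Expected pre-post change = package effect + drift, where drift = monthly rate × months. Both the rates and their upward direction are assumptions.

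- Month 3: 0.02 × 3 = 0.06 SD; 0.05 × 3 = 0.15 SD.
- Month 9: 0.02 × 9 = 0.18 SD; 0.05 × 9 = 0.45 SD.

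For a two-point paired test with n = 50, SE = √(2(1 − r)/50). At r = 0.5 this is √0.02 = 0.141 SD. Suppose the package has no effect and the test is two-sided at 5% (assumed). The chance of a significant result is Φ(d/SE − 1.96) + Φ(−d/SE − 1.96), where d is the drift:

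- d = 0: 5%.
- d = 0.2 SD: 22%, 29% and 45% at r = 0.3, 0.5 and 0.7.
- d = 0.3 SD: 43%, 56% and 78% at the same correlations.

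The planned analysis is a growth model over all waves, so these percentages show the mechanism and do not predict the trial's error rate.

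**4. The ORS/SRS model**

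Section 5.3.1 includes a fixed effect for whether the clinician's agency is in the intervention or the control condition, and time periods MP1, 2 or 3. MP is not defined in the text reviewed. No control agency is described, all clinicians receive the same supports, and section 4.1.1 places the student baseline after the first training session. No student data under a control condition are described, so the term cannot be fitted as written.

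**The case against.** The strongest reply is that the plan is open about what it does. Section 4.1.1 says there is no random assignment, that all clinicians get the same supports, and that the primary comparison is pooled pre-post. Section 3.1 already words the hypotheses as increases relative to baseline and admits that the pilot is underpowered. Section 5.3.1 reports 95% confidence intervals and sets no success criterion. All of that stands, and it confines the overclaim to the label and the wording of the objective. The power caveat concerns precision, however. It does not say that change is confounded with time.

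The second reply is that a stagger exists. There are fall 2021 and fall 2022 cohorts, and a control period with only a minimum length permits unequal baselines. It would indeed be wrong to say that every clinician starts in the same season. But the cohorts are not assigned by district, each is followed only in its own year, and no model uses the offset.

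Three stronger readings are tempting and are not supported:

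- That the sentence "This allows clinicians in the two school districts to be compared to each other and to their own baseline" offers districts as controls. It does not say so, and between-agency differences are listed only as a secondary comparison.
- That drift could equal the effect, because 0.45 SD exceeds the change detectable with 80% power in a paired test (2.8 × 0.141 = 0.40 SD at r = 0.5). That sets an assumed drift against a detection limit, not against an effect. It uses a test the plan does not propose, and only the highest assumed rate at month 9 passes it.
- That the study can say nothing about any outcome. Fidelity is coded monthly from records in a system whose access comes with the project (Table 1; section 5.2). Retest and expectancy in self-ratings do not carry over simply to recorded use.

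**Conclusion.** The point holds for clinician ratings. As described, the primary analysis is a single-group pre-post comparison under a multiple-baseline label. It can estimate change from baseline at 3, 6 and 9 months. It cannot attribute that change to the package rather than to school-year trend, retest or expectancy.

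The structural conclusion rests on the documents: one pre-training survey, no district-specific starts, the same supports for all, and no condition term in the primary model. The size rests on assumption. The 0.18 to 0.45 SD by month 9 is illustrative, and the documents give nothing to narrow it. A reader might infer that the supports do not work, or that the observed change will be mostly drift. Neither follows.

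The text that should be section 4.1.3 (number of study sites) was not available for this check. If it gives district start dates, the last item of the fix applies. This should be corrected, in proportion to a self-declared pilot.

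**What to change.** 1. In the Synopsis and section 4.1.1, describe the design as single-group pre-post with 3-, 6- and 9-month follow-up.
2. Keep between-district differences as a descriptive secondary comparison, and say that they are not a control.
3. In the Synopsis and section 3.2, change the primary objective to estimating the change from baseline in implementation outcomes. State that this change cannot be separated from secular trend or retest. The hypotheses in section 3.1 already speak of change from baseline and need no rewording on this point.
4. In section 5.3.1, remove the intervention-or-control term and the MP1, 2 or 3 periods from the ORS/SRS model, or define them and reconcile them with the statement that all clinicians receive the same supports.
5. If districts did start at different times, state the dates and add a calendar-time term to the model. Note that one baseline survey per clinician still limits attribution.

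The cost is protocol wording, submitted to the IRB as section 6.11 requires. No new data are needed. The downside is that the stated conclusion becomes less favourable.
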